## PROTOCOL SYNOPSIS

TITLE	TEACH Trial: T esting the E ffect of A dding C Hronic Azithromycin to Inhaled Tobramycin. A randomized, placebo-controlled, double-blinded trial of azithromycin 500mg thrice weekly in combination with inhaled tobramycin
SPONSOR- INVESTIGATOR	[name] (Seattle Children's Hospital)
FUNDING ORGANIZATION	National Institutes of Health/National Heart, Lung, and Blood Institute Cystic Fibrosis Foundation Therapeutics, Inc. (CFFT)
NUMBER OF SITES	Approximately 40
RATIONALE	Patients with cystic fibrosis (CF) commonly acquire a chronic airway infection with Pseudomonas aeruginosa ( Pa ). Both inhaled tobramycin and oral azithromycin have been proven beneficial in these patients and are currently used by the majority of eligible patients. 75% of US patients prescribed inhaled tobramycin are also prescribed chronic oral azithromycin. We believe that azithromycin may be inhibiting the anti- Pa effects and clinical benefits of inhaled tobramycin in clinically infected patients. This study is designed to compare monotherapy with inhaled tobramycin versus combination therapy adding chronic oral azithromycin to inhaled tobramycin.

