
Rationale for Number of Subjects
	
The primary endpoint is the difference between the azithromycin and placebo treatment groups in the relative change from Visit 1 to Visit 3 in FEV1 (liters). Data from prior published studies of similar duration are available to estimate sample size and power for the study including a randomized, placebo-controlled trial of azithromycin in individuals with CF chronically infected with Pa and a randomized, placebo controlled trial of aztreonam lysine similarly among those with chronic Pa. These studies suggest a standard deviation of the relative change in FEV1 ranging from 10 to 16. Based on these prior studies, we anticipate the relative change in FEV1 from Visit 1 to Visit 3 to be -2% in the azithromycin arm and +6.85% in the placebo arm for an overall treatment effect of 8.65%. A sample size of 110 provides 85% power to detect a treatment effect of 7.5% or greater assuming a standard deviation of 13. 110 subjects provides 93% power to detect a treatment effect similar to what was observed in the preliminary data (8.65%) assuming a standard deviation of 13. It is noteworthy that the standard deviation from more recently completed studies CF studies have observed standard deviations in short term relative change in FEV (liters) ranging from 8-11, confirming our conservatism in the standard deviation estimate used for our sample size calculations. Assuming a standard deviation of 11, a sample size of 110 provides 85% power to detect a treatment effect of 6.3% or greater in favor of the placebo group.
 
It is anticipated from prior CF trials conducted through the TDNCC that the attrition rate will be less than 10%, and thus a sample size of 120 will ensure at least 110 subjects will complete the trial.

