## 8 STUDY TREATMENTS

### 8.1 Randomization

At Visit 1, eligible subjects will be enrolled and randomized to study drug. Study personnel at the investigative site will use the Medidata® Rave and Balance™ systems to randomize each subject. An adaptive randomization (dynamic allocation based on minimization) will be employed. Subjects will be randomly assigned in a 1:1 ratio to azithromycin (500 mg three times per week) or matched placebo. Randomization will be stratified by FEV1 % predicted (25%-50%, >50%-75%, >75%), chronic oral azithromycin use for the past 30 days, inhaled tobramycin formulation (TIS or TIP), and site. The dynamic allocation algorithm seeks to optimize randomization balance by minimizing a weighted average of the marginal imbalance of treatment allocation for each factor and for the study overall. A random element is added to the otherwise deterministic minimization algorithm to reduce allocation predictability by using a biased coin to include a chance of allocation to a treatment arm other than the arm that optimizes balance. After data collection at Visit 1, subjects will be randomized to one of the two treatment groups. To randomize a new subject, study personnel at the investigative site will complete the electronic CRF in the Medidata Rave system required to provide the stratification information and the subject will then be assigned to a treatment group.

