### 15.3 Analysis of Primary Endpoint

The primary endpoint will be the difference between the azithromycin and placebo treatment groups in the relative change from Visit 1 to Visit 3 in FEV1 (liters). The primary endpoint will be compared between treatment groups using linear regression adjusted for randomization strata. Least squares means and the treatment effect for the relative change will be presented as well as corresponding 95% confidence interval and p-values. The p-values will be evaluated against a two-sided 0.05 level of significance.

Additional secondary analysis may be performed to adjust for potential baseline confounders including age, sex, and baseline FEV1. Sensitivity analyses of the primary endpoint will be performed using the per-protocol population. Additional sensitivity analyses will be performed to address missing data. Specifically, the least favorable treatment arm imputation method will be used which imputes that missing value with the mean change from the treatment arm with the worst change in the observed case analysis. Further details regarding the handling of missing data will be provided in the statistical analysis plan.

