### 15.6 Sample Size

The primary endpoint is the difference between the azithromycin and placebo treatment groups in the relative change from Visit 1 to Visit 3 in FEV1 (liters). Data from prior published studies of similar duration are available to estimate sample size and power for the study including a randomized, placebo-controlled trial of azithromycin in individuals with CF chronically infected with *Pa* and a randomized, placebo controlled trial of aztreonam lysine similarly among those with chronic *Pa*. These studies suggest a standard deviation of the relative change in FEV1 ranging from 10 to 16. Based on these prior studies, we anticipate the relative change in FEV1 from Visit 1 to Visit 3 to be -2% in the azithromycin arm and +6.85% in the placebo arm for an overall treatment effect of 8.65%. A sample size of 110 provides 85% power to detect a treatment effect of 7.5% or greater assuming a standard deviation of 13. 110 subjects provides 93% power to detect a treatment effect similar to what was observed in the preliminary data (8.65%) assuming a standard deviation of 13. It is noteworthy that the standard deviation from more recently completed studies CF studies have observed standard deviations in short term relative change in FEV (liters) ranging from 8-11, confirming our conservatism in the standard deviation estimate used for our sample size calculations. Assuming a standard deviation of 11, a sample size of 110 provides 85% power to detect a treatment effect of 6.3% or greater in favor of the placebo group. Figure 8 displays several scenarios for the statistical power we have to detect a range of differences in relative change in FEV1 (L).

**Figure 8. Power to detect a range of differences in relative change in FEV1 (L) for total sample size of 110 (55 per group) assuming a two-sided 0.05 level t-test. Curves (in ascending order) correspond to standard deviations of 15, 13, 11, 9, and 7.**

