The incidence of AEs (including emergent abnormal QTc parameters) between the azithromycin and placebo treatment groups is tabulated by seriousness, severity, and relationship to study drug. The proportion of participants with at least one (S)AE, the average number of (S)AEs per patient, and the rate of (S)AEs per day of follow-up are reported. Poisson regression modeling is used to derive rate ratios and corresponding 95% confidence and to compare groups using a two-sided 0.05 level test. The difference in the proportion of participants experiencing at least one (S)AE between treatment groups is also reported, with corresponding 95% confidence intervals calculated using the Newcombe-Wilson method and p-values derived from a Fisher's exact test. Histograms showing the frequency of the number of (S)AEs in each treatment group are included.

All reported SAEs and AEs are coded using MedDRA and grouped by body system. Detailed summary tables of individual (S)AEs grouped by SOC are included to show the number and percent of participants experiencing each (S)AE by treatment group. The number and rate of events for each (S)AE is also reported by treatment group. Poisson regression is used to derive rate ratios and corresponding 95% confidence intervals comparing treatment arms for each SOC. Treatment groups are compared by the proportion of participants experiencing (S)AEs by System Organ Class (SOC) as well as the difference in proportions with corresponding 95% confidence intervals to compare treatment arms.

All SAE narratives are included in a listing appended to this report.

A.5 Summary of Spirometry Results

The primary endpoint is the difference between the azithromycin and placebo treatment groups in the relative change from Visit 1 to Visit 3 in FEV1 (liters). The primary efficacy analysis is conducted on the m-ITT population and repeated on per-protocol population. Predicted values for spirometry measures at each visit are calculated using the Global Lung Initiative reference equations.

A linear regression model adjusted for randomization strata is used to compare the primary endpoint between treatment groups. Least squares means and the treatment effect are presented

along with corresponding 95% confidence intervals and p-values. The primary analysis is adjusted for the group sequential monitoring.

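### The primary model adjusts for strata that include about 40 sites without saying how site enters; as fixed effects, power may be about 71–79% rather than the stated 85%

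*SAP*

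**What the plan says.** Protocol 15.3: "The primary endpoint will be compared between treatment groups using linear regression adjusted for randomization strata". SAP A.5 repeats this: "A linear regression model adjusted for randomization strata is used to compare the primary endpoint between treatment groups". SAP A.7 (weight) and A.8 (CFRSD-CRISS and CFQ-R respiratory scale) use the same adjustment, and protocol 15.4 models the continuous secondary endpoints like the primary.

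Protocol 8.1 lists the factors as FEV1 group (three levels), "chronic oral azithromycin use for the past 30 days, inhaled tobramycin formulation (TIS or TIP), and site". Allocation is by "minimizing a weighted average of the marginal imbalance" over each factor and the study overall, with a biased coin. The factor weights and the coin probability are not given. The synopsis puts the number of sites at "Approximately 40" and says "a sample size of 120 will ensure at least 110 subjects will complete the trial".

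On power, protocol 15.6 says "A sample size of 110 provides 85% power to detect a treatment effect of 7.5% or greater assuming a standard deviation of 13" and "Assuming a standard deviation of 11, a sample size of 110 provides 85% power to detect a treatment effect of 6.3% or greater". The Figure 8 caption gives the basis as a two-sided 0.05 t-test with 55 per group. SAP 1.3 repeats the 85% and gives a final boundary of -4.9% and interim boundaries of ±9.8%. It says the actual boundaries will be recomputed at the interim according to the number of evaluable subjects.

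No sentence in either text says whether site is fixed, random, pooled or left out.

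**The concern.** Site is named among the strata and the model is called linear regression, so fixed site effects are the literal reading. A random intercept would be a mixed model, which neither document names. Omitting site departs from the stated adjustment. Yet the power and boundary figures assume no site terms at all.

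With about 110/40 = 2.75 completers per site, many sites will be unbalanced between arms and some will have only one arm. A fixed-effects fit compares arms only within sites, so one-arm sites contribute nothing to the treatment estimate.

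Two things are at stake. The primary model can still be chosen among versions with different power, possibly after data are seen. And under the literal version the trial may have less power than stated.

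**Working it through.** **1. Reproduce the stated figures.** Inputs from protocol 15.6 and SAP 1.3: 55 per arm, two-sided 0.05. SE = SD × √(2/55); power from the noncentral t with 108 df.

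- 7.5% at SD 13: SE = 13 × 0.1907 = 2.479; 7.5/2.479 = 3.025; power 85.0% (stated 85%).
- 6.3% at SD 11: SE = 2.098; ratio 3.003; power 84.5% (stated 85%).
- 8.65% at SD 13: ratio 3.489; power 93.3% (stated 93%).
- Final boundary: 2.479 × 1.977 = 4.90. Interim boundary: 13 × √(2/27.5) × 2.797 = 3.506 × 2.797 = 9.81.

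All agree with the plan, so all rest on a comparison without site terms.

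**2. Put site in as fixed effects.** Minimization on the four factors plus overall balance was simulated: 120 randomized, 110 completers at random. The documents do not give these settings, so they are assumptions: coin 0.8 or 0.95; site weight one or four times the others; accrual from equal to strongly skewed; FEV1 groups 35/40/25%; prior azithromycin 70%; powder 35%. Strata explain no variance.

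With 40 sites, the information on treatment was 0.71–0.87 of the balanced value (55 × 55/110 = 27.5). Residual df were 67–76, and 9–22 participants were in one-arm sites. For 7.5% at SD 13, combining the extremes:

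- Low end: SE = 2.479/√0.71 = 2.942; ratio 2.549; 67 df; power 71.0%.
- High end: SE = 2.479/√0.87 = 2.658; ratio 2.822; 76 df; power 79.6%.

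Averaged over simulated trials within each scenario:

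| Effect, SD | No site terms (t-test) | 40 fixed sites | 30 fixed sites |
|---|---|---|---|
| 7.5%, 13 | 85.0% | 71–79% | 75–81% |
| 6.3%, 11 | 84.5% | 70–79% | 75–81% |
| 8.65%, 13 | 93.3% | 82–89% | 86–91% |
| 7.5%, 11 | 94.3% | 84–91% | 88–92% |

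Other settings (coin 0.8–1.0, site weight 1 or 3) gave about 70–80% at 40 sites and 67–82% over 30–45 sites for 7.5% at SD 13. The cause is mainly lost within-site contrast: cutting df to about 65 alone leaves 84.6%.

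**3. Let site explain variance** (40 sites, 7.5%, SD 13, two extreme settings, 4,000 runs each):

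| Site share of variance | Fixed-site power |
|---|---|
| 0% | 71–79% |
| 5% | 73–82% |
| 10% | 74–83% |
| 20% | 80–87% |

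Over the same shares, omitting site gave 85–87% (type I error 3.9–5.0%). A random intercept (REML, 104 df) gave 85–90% (type I error 4.7–5.7%).

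If instead the other three strata explain variance, step 2 with the SD multiplied by √(1 − R²) gives 75–84% at R² = 0.10 and 80–88% at R² = 0.20.

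**4. Patient-reported scores.** Both are collected at Visit 1 (protocol 10.1), but SAP A.8 names no baseline score in the change models. With equal variances and Visit 1–Visit 3 correlation ρ, the variance with the covariate relative to the change score is (1 + ρ)/2: 0.75 at ρ = 0.5 and 0.90 at ρ = 0.8, a fall of 25% to 10%. These correlations are assumed.

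**5. Effect size.** 6.85 − (−2) = 8.85, but the synopsis and 15.6 state 8.65. At SD 13, 8.85% gives 94.3% power and 8.65% gives 93.3%.

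**The case against.** The strongest reply is that nothing here shows the 85% to be wrong. Two of the three ways of handling site deliver it, and the shortfall under the third depends on settings the documents do not give. This stands. A reader might infer that the trial is underpowered as designed, but the documents do not support that, because they do not say fixed sites will be used.

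A reader might also infer that both 85% statements must fail under fixed sites. They need not: at a 20% site share, power for 7.5% at SD 13 is 80–87%. The zero-variance case is close to the worst one.

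The protocol calls SD 13 conservative and reports recent SDs of 8–11. If SD is 11, power for 7.5% is 84–91% even with 40 fixed sites, so the practical risk for that effect is smaller. The separate claim of 85% for 6.3% at SD 11 is not rescued in this way when the strata explain little.

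SAP A.5 lists azithromycin use, formulation and baseline FEV1, but not site, as covariates for sensitivity summaries. That is weak support for a model without site and does not define the primary one. SAP 1.2 refers to table shells that the public text does not show; whether they name model terms cannot be checked.

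Finally, the boundaries are to be recomputed at the interim. That helps, but the stated trigger is the number evaluable, not the model's information. No inflation of type I error should be inferred: with critical values 2.797 and 1.977 kept, it is 0.0500, 0.0506 and 0.0512 at information fractions 0.50, 0.41 and 0.32.

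**Conclusion.** The concern holds as a gap in specification with a conditional cost. The literal model does not deliver the stated 85% when site and the other strata explain little variance: about 71–79% for 7.5% at SD 13 with 40 fixed sites, and about 70–79% for 6.3% at SD 11. The direction is firm; the exact range depends on the assumed coin, weights, accrual and number of enrolling sites. The loss shrinks, and may vanish, when strata explain roughly 20% of variance. Omitting site or fitting it as random keeps about 85%.

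The patient-reported analyses are valid as planned but less precise than the collected data allow. The 8.65% and 8.85% figures conflict, but it should not be inferred that 8.85% is right: the text ties 8.65% to preliminary data, so an arm value may be the slip. The discrepancy is worth one point of power and does not touch the 7.5% target.

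**What to change.** - **Model terms.** In protocol 15.3 and SAP A.5, A.7 and A.8, name additive effects of FEV1 group, azithromycin use in the past 30 days and tobramycin formulation, and state how site is handled. Either of two choices keeps the stated power: omit site, with a reason; or fit a random site intercept, with a named degrees-of-freedom method and a rule for zero site variance or non-convergence.
- **If fixed sites are intended.** Restate the power for that model in the synopsis, 15.6 and SAP 1.3, and base the recomputed boundaries on the model's actual information, not only on the number evaluable.
- **Patient-reported scores.** Add the Visit 1 score as a covariate in the CFRSD-CRISS and CFQ-R change models.
- **Effect size.** Reconcile the arm changes with the stated effect in the synopsis and 15.6, and give the power that matches.

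None of this needs new data or visits. Omitting site and adding the Visit 1 score need only wording. The random intercept changes the primary analysis from linear regression to a mixed model. Keeping fixed sites needs a revised power statement.

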## 12 DISCONTINUATION AND REPLACEMENT OF SUBJECTS

### 12.1 Early Permanent Discontinuation of Study Treatment

A subject may be permanently discontinued from study treatment at any time if the subject, the investigator, or the Sponsor-Investigator feels that it is not in the subject's best interest to continue. The following is a list of possible reasons for early permanent discontinuation of study treatment:

- Subject or subject's legal representative decision
- Adverse event, including pulmonary exacerbation
- Protocol violation
- Death

If a subject is discontinued from treatment due to an AE, the subject will be followed and treated by the site investigator until the abnormal parameter or symptom has resolved or stabilized.

All subjects who permanently discontinue study treatment early should come in for an early discontinuation of study treatment visit as soon as possible (see Appendix 1) and then should be encouraged to complete all remaining scheduled visits and procedures.

Refer to Section 8.6.2 for temporary discontinuation of study drug.

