1.1 Study Rationale and Design

Patients with cystic fibrosis (CF) commonly acquire a chronic airway infection with *Pseudomonas aeruginosa* (*P.a.*). Both inhaled tobramycin and oral azithromycin have been proven beneficial in these patients and are currently used by the majority of eligible patients. Seventy five percent of US patients prescribed inhaled tobramycin are also prescribed chronic oral azithromycin. We believe that azithromycin is inhibiting the anti-*P.a.* effects and clinical benefits of inhaled tobramycin. This study will investigate whether azithromycin is associated with poorer clinical and microbiologic outcomes as compared to placebo during concurrent administration of inhaled tobramycin.

This is a prospective, randomized, placebo-controlled, double-blinded study of azithromycin in subjects with chronic *Pa* airway infection using inhaled tobramycin. Subjects who have received two (2) or more cycles of inhaled tobramycin within the 24 weeks prior to enrollment will be recruited into the study. Approximately 120 eligible subjects (allowing for 10 withdrawn) will be enrolled and randomized to either azithromycin or placebo at Visit 1 (Day -14), approximately 14 days prior to the start day of their next planned 28-day nebulized solution or dry powder tobramycin (TISP) cycle. Subjects will be randomized in a 1:1 fashion to azithromycin (500 mg three times per week) or matched placebo.

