1.3 Statistical Monitoring Guidelines and Stopping Rules

While there are no pre-determined stopping rules for safety, the DSMB may decide to stop the study either temporarily or permanently if there are significant concerns regarding subject safety. There is however pre-specified stopping rule for efficacy/harm and futility with respect to the primary endpoint.

Should the DSMB consider stopping the trial based on the primary endpoint, they will be guided by a formal stopping rule to be assessed when approximately 50% of patients have completed the randomized portion of the trial. The primary endpoint is the difference between the azithromycin and placebo treatment groups in the relative change in FEV₁ (liters) from randomization at Visit 1 (Day -14) to Visit 3 (Day 28). We hypothesize that azithromycin is associated with poorer clinical outcomes (inferiority) as compared to placebo during concurrent administration of inhaled tobramycin and thus there will be a smaller improvement or a worsening in FEV₁ in the azithromycin treatment group as compared to placebo treatment from Visit 1 (Day -14) to Visit 3 (Day 28). Assuming a sample size of 110 subjects, two-sided type 1 error of 0.05, and a standard deviation for the relative change of 13%, the study has approximately 85% power to detect a difference (relative change in FEV₁ in the azithromycin treatment group minus the relative change in FEV₁ in the placebo treatment group) of less than or equal to -7.5% (e.g. azithromycin is clinically inferior to placebo).

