The primary endpoint is also summarized descriptively as a plot of average values in each treatment group at each post-randomization visit accompanied by 95% confidence intervals (using t-distribution approximation).

Additional secondary analysis may be performed to adjust for potential baseline confounders including age, sex, use of CFTR modulators, and baseline FEV1. To address missing data, the least favorable treatment arm imputation method is used to impute that missing value with the mean change from the treatment arm with the worst change in the observed case analysis. In further sensitivity analyses, the primary endpoint is summarized for a select number of baseline covariates including age, sex, baseline FEV1, chronic azithromycin use, and inhaled tobramycin formulation.

The exploratory spirometry endpoints, i.e. absolute change from Visit 1 to Visit 3 in FEV1 (liters and % predicted), absolute and relative change in FVC (liters and % predicted), and absolute and relative change in FEF25-75% are summarized descriptively as plots of mean values and corresponding 95% confidence intervals over time.

Additionally, changes in spirometry measures from Visit 1 to Visit 3 and Visit 2 to Visit 3 are modeled using linear regression adjusted for randomization strata. The estimates of least squares means, differences in the least squares means between the treatment groups, and corresponding 95% confidence intervals and p-values are presented.

All of the spirometry measures are summarized at each study visit during the randomized period and as a change from Visit 1 and Visit 2. The differences between treatment groups are presented with accompanying 95% confidence intervals and p-values calculated using two-sample t-tests.

Post-hoc comparisons of participants responding and not responding to monotherapy are summarized. Several 'responder' definitions are considered, e.g. XX% or greater relative increase in FEV1 % predicted from Visit 1 to Visit 3, XX% or greater relative increase in FEV1 % predicted from Visit 2 to Visit 3, 11 or greater point decline in CFRSD-CRISS from Visit 1 to Visit 3, and a XX point increase in CFQ-R respiratory symptom scale.

A.6 Pulmonary Exacerbations, Hospitalizations and Antibiotic Usage

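### The only named missing-data check on the primary endpoint fills every gap with the worse arm's mean: it nearly repeats the observed-case test when losses are balanced and is anti-conservative when they fall mainly on the worse arm

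*SAP*

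**What the plan says.** Protocol 15.3 promises sensitivity analyses for missing data and names one: "Specifically, the least favorable treatment arm imputation method will be used". It defines this as a method that "imputes that missing value with the mean change from the treatment arm with the worst change in the observed case analysis", and adds: "Further details regarding the handling of missing data will be provided in the statistical analysis plan".

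SAP Appendix A.5 gives no further detail. It restates the rule ("used to impute that missing value with the mean change from the treatment arm with the worst change") and names no multiple imputation, repeated-measures model, delta adjustment or variance correction. The per-protocol repeat and the summaries by baseline covariate are other sensitivity analyses, but neither deals with missing values.

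The primary model is given as "A linear regression model adjusted for randomization strata is used to compare the primary endpoint between treatment groups". SAP 1.3 states the expected direction: "We hypothesize that azithromycin is associated with poorer clinical outcomes (inferiority) as compared to placebo during concurrent administration of inhaled tobramycin". SAP 1.1 plans for modest loss: "Approximately 120 eligible subjects (allowing for 10 withdrawn) will be enrolled".

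**The concern.** The rule treats both arms alike. Any missing Visit 3 change, whichever arm it comes from, becomes the observed mean of the worse arm. Three consequences follow.

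- **Losses mainly on the worse arm.** Those subjects receive their own arm's mean. The estimate does not move, while the analysis gains subjects who add no spread, so the SE is too small.
- **Balanced losses.** The estimate and the SE shrink by nearly the same factor, and the test hardly changes.
- **Losses mainly on the better arm.** The estimate is pulled toward zero by more than the SE shrinks. Only here is the check stricter than the observed-case test.

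The trial sets out to show azithromycin inferiority. If azithromycin is the worse arm, the assumption that could overturn that conclusion is that its missing subjects did better than its observed ones. The rule never tests it. A check labeled least favorable could therefore make the finding look firmer than the primary analysis does.

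The rule as written also makes no use of the subject's own Visit 2 spirometry (Protocol 10.2) or of spirometry at the early-discontinuation visit (Protocol 10.6). Protocol 12.1 asks for that visit: "All subjects who permanently discontinue study treatment early should come in for an early discontinuation of study treatment visit as soon as possible".

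**Working it through.** **Inputs.** SD 13, 55 evaluable per arm and two-sided 0.05 are from Protocol 15.6. The 120 randomized and 10 lost are from SAP 1.1, and 1:1 allocation is from Protocol 8.1, giving 60 per arm. The split of losses is not in the documents, so a range is shown as azithromycin/placebo, with azithromycin the worse arm. The p-values are nominal, without sequential adjustment.

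**The plan's own figure.** 7.5 / (13 × √(2/55)) = 3.025. The noncentral t with 108 df gives 85.0% power, as stated.

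**Closed form.** Let an arm have n observed and k missing values, observed mean m and SD s, and let w be the worse arm's mean. After imputation:

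- mean M = (n·m + k·w)/(n + k)
- sum of squares SS = (n − 1)s² + [nk/(n + k)](m − w)²
- SE = √[(SS_A + SS_P)/118 × 2/60]

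*10/0.* Observed-case SE = 13√(1/50 + 1/60) = 2.489. After imputation SS_A = 49 × 169 = 8,281 and SS_P = 59 × 169 = 9,971. SE = √(18,252/118/30) = 2.271, with the difference unchanged.

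*5/5, observed -7.5, placebo mean set to 0.* M_P = 5 × (−7.5)/60 = −0.625, so the difference is −6.875. SS_A = 54 × 169 = 9,126 and SS_P = 9,126 + (275/60) × 56.25 = 9,383.8. SE = √(18,509.8/118/30) = 2.287.

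| Losses (azi/pbo) | Observed difference | After rule | SE before → after | p before → after |
|---|---|---|---|---|
| 5/5 | -7.5 | -6.88 | 2.479 → 2.287 | 0.0031 → 0.0032 |
| 5/5 | -4.9 | -4.49 | 2.479 → 2.278 | 0.0506 → 0.0509 |
| 8/2 | -4.9 | -4.74 | 2.483 → 2.274 | 0.051 → 0.039 |
| 10/0 | -4.7 | -4.7 | 2.489 → 2.271 | 0.062 → 0.041 |
| 10/0 | -4.9 | -4.9 | 2.489 → 2.271 | 0.052 → 0.033 |
| 10/0 | -5.0 | -5.0 | 2.489 → 2.271 | 0.047 → 0.030 |
| 0/10 | -5.0 | -4.17 | 2.489 → 2.284 | 0.047 → 0.071 |

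The value -4.9 is the SAP's final rejection boundary. If the 10 missing azithromycin subjects in the 10/0 case were given the placebo mean instead, -5.0 would become -5.0 × 50/60 = -4.17, p = 0.071.

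**Simulation with strata.** 10,000 trials per scenario, true effect -5, losses completely at random. The regression used FEV1 band, prior azithromycin use and tobramycin formulation; site was omitted, and stratum shares and effects were assumed.

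| Losses (azi/pbo) | Coverage, rule | Rejection, rule vs observed-case |
|---|---|---|
| 10/0 | 92.8% | 57.3% vs 50.2% |
| 8/2 | 93.7% | 55.3% vs 50.6% |
| 5/5 | 94.7% | tests disagree in 2.0% of trials |
| 0/10 | not reported | 42.5% vs 50.5% |

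At 10/0 the mean SE is 2.29 against an actual SD of 2.49, so 8% too small. At 5/5 it is 2.30 against 2.29.

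**Under the null.** Rejection is 5.0–5.4% in every split. This hides an asymmetry. In a separate run without strata (400,000 trials, 10/0), the azithromycin-worse tail is 0.0365 and the other tail 0.0156, each against 0.025. The inflated tail is the hypothesized direction.

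**Tipping point.** Suppose missing azithromycin subjects did δ better than observed ones and the SE stays at its observed-case value. Significance is lost when δ = (|d| − 1.982 × SE) × 60/k. At 10/0 the threshold is 1.982 × 2.489 = 4.934, so an observed -5.5 tips at (5.5 − 4.934) × 6 = 3.4 points, -6.0 at 6.4 and -7.5 at 15.4. At 5/5 the values are 7.0, 13.0 and 31.0.

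**The case against.** The strongest case against concerns weight, not arithmetic.

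- **The split is assumed.** If each of 10 losses is equally likely in either arm, at least 8 fall on azithromycin with probability 5.5%, and all 10 with probability 0.1%. With losses scattered at random (4,000 trials, true effect -5), rejection is 50.5% under the rule against 50.7% observed-case, with coverage 94.7%. This stands. The anti-conservatism is conditional on uneven losses.
- **The direction of losses is open.** Every participant has used azithromycin before (inclusion criterion 11), so first-exposure intolerance is not expected. Protocol 2.1 names withdrawal of azithromycin as a possible harm, which could put losses on placebo and make the rule stricter. Against that, the Background reports more additional antibiotic use among azithromycin users. Neither direction is established.
- **The plan limits missing data.** Subjects who stop study drug are encouraged to attend remaining visits and stay in the analysis, and missing spirometry at Visits 1–3 is a protocol violation. This reduces the scale of the problem without repairing the check.
- **Site was left out of the simulation.** Site is a randomization factor. With 40 site effects added, disagreement at 5/5 rises to about 6%, so near-repetition is less exact than 2.0% suggests. The inflation at 10/0 persists (42.7% against 35.7% in one run, 42.1% against 34.1% in another).
- **Early-discontinuation spirometry.** Neither document says whether it may stand in for Visit 3. That is an unspecified detail, and the main point does not depend on it.
- **Multiple imputation also tracks observed cases.** True. The tipping-point analysis supplies the stress.

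A sensitivity analysis is needed most for near-boundary results and uneven losses, and that is where this one fails.

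**Conclusion.** The concern holds. The single named method understates the SE when losses fall mainly on the worse arm, by 8% at 10/0. It adds almost nothing to the observed-case test when losses are balanced. It does not test the assumption that matters if azithromycin is the worse arm.

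The size is modest. The primary m-ITT analysis does not change, overall two-sided error stays near 5%, and about 10 of 120 subjects are expected to be lost. At the design effect of -7.5 the conclusion would survive any plausible check. Nearer the -4.9 boundary, the rule can move a result from non-significant to significant with no new data.

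The figures rest on SD 13, 60 per arm, assumed splits and, in the simulations, assumed stratum effects and losses completely at random. This should be corrected, but it does not threaten the trial's primary result.

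**What to change.** In SAP Appendix A.5, before unblinding, replace the single-mean rule with two analyses:

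1. **Multiple imputation by arm**, using Visit 1 and Visit 2 FEV1, early-discontinuation spirometry where available, and the FEV1, azithromycin-use and formulation strata, combined by Rubin's rules. State when a Visit 3 value counts as missing and how early-discontinuation spirometry enters.
2. **A delta-adjusted tipping-point analysis** applied to each arm in turn, reporting the shift at which the conclusion changes.

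The first restores the variance. In 3,000 simulated trials (20 imputations, true effect -5, losses 10/0), coverage was 95.3% with an assumed Visit 2 correlation of 0 and 95.5% with 0.6, against 92.8% and 92.9% for the rule. Rejection was 49.4% and 50.4%, against 57.3% and 56.2%. The second supplies the departure from missing at random that the current rule omits.

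The cost is SAP wording, some programming and slightly wider sensitivity intervals. The primary analysis and sample size do not change.
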